#### 3.2 Secondary Objective(s)

Individuals with mild VCI also show deficits in processing speed, memory and working memory. Our secondary goal is to evaluate the therapeutic potential of NAC to enhance the effect of exercise on additional cognitive domains in these patients. We hypothesize that:

- In patients with mild VCI, those randomized to NAC (2,400 mg/day) will demonstrate greater improvement in processing speed over 24 weeks as compared to placebo.
- In patients with mild VCI, those randomized to NAC (2,400 mg/day) will demonstrate greater improvement in memory over 24 weeks as compared to placebo.
- In patients with mild VCI, those randomized to NAC (2,400 mg/day) will demonstrate greater improvement in working memory over 24 weeks as compared to placebo.

Processing speed will be based on the Symbol Digit Modalities Test and the memory domain, will consist of the Rey Complex Figure Test-immediate/delayed recall and recognition and Hopkins Verbal Learning Test (HVLT) -immediate/delayed recall and recognition, found in the 60-minute battery recommended by the NINDS-CSN. Working Memory will be based on Digit Span test (Forward, Backward, and Sequencing subtests).

NAC crosses the blood brain barrier and acutely increases blood and brain GSH concentrations. To demonstrate target engagement, we aim to evaluate the effect of NAC on the GSH antioxidant system and OS. The antioxidant levels will be evaluated by measuring levels of glutathione peroxidase (GPx), glutathione reductase (GR) and glutathione S-transferases (GST). OS will be quantified by measuring concentrations of late markers (e.g., 8-ISO and 4-HNE) and early marker (LPH) lipid peroxidation products. LPH is one of the primary and earliest products of lipid peroxidation, which are inherently unstable and susceptible to further free radical-mediated

reactions, which results in the generation of late-stage oxidative stress products. Higher OS will be indicated by higher ratio between late marker (e.g., 8-ISO) and early marker (LPH) of lipid peroxidation as supported by our pilot data.

- In patients with mild VCI, the plasma levels of GPx, GR and GST will be significantly higher in those receiving NAC supplementation relative to those who received exercise intervention alone.
- In patients with mild VCI, the 8-ISO to LPH ratio will be significantly lower in those receiving NAC supplementation relative to those who received exercise intervention alone

Evidence from neuroimaging studies in VCI patients indicated greater severity and progression of white matter lesion burden was associated with greater declines in executive function and processing speed. We will investigate whether baseline WMH severity significantly predicts the cognitive response to NAC.

- In patients with mild VCI, those with lower WMH volume at baseline will demonstrate greater cognitive improvement in response to 24 weeks of NAC treatment

Previous trials have shown that NAC at these doses is well-tolerated in the elderly. We will investigate tolerability of NAC.

- In patients with mild VCI, measures of safety (including incidences of adverse events and drop-outs) will be comparable between treatment with NAC and placebo.

### **3.3 Exploratory Hypotheses**

The antioxidant defense molecule GSH serves as the primary antioxidant in the brain by scavenging harmful reactive oxygen species generated during cellular metabolism. GSH depletion plays an important role in OS-mediated neuronal death, precedes neurodegeneration, and contributes to the etiology of various neurodegenerative diseases. Advances in magnetic resonance spectroscopy (MRS) now allow *in vivo* non-invasive quantification of GSH in the brain. We propose an innovative methodology to investigate the association between brain GSH and cognitive performance in subjects with mild VCI who are likely to have higher oxidative stress and GSH depletion.

- In these patients, those with higher GSH levels at baseline will demonstrate greater improvement in executive function over 24 weeks.
- In these patients, those with higher GSH levels at baseline will demonstrate greater improvement in processing speed over 24 weeks.
- In these patients, those with higher GSH levels at baseline will demonstrate greater improvement in memory over 24 weeks.
- In these patients, those with higher GSH levels at baseline will demonstrate greater improvement in working memory over 24 weeks.

Apathy is a prominent neuro-behavioral symptom of vascular dementia; it is defined as an impairment in motivation that persists over time. Unfortunately, apathy has rarely been assessed in mild VCI. We propose to assess apathy in these patients using the Apathy Evaluation Scale (AES) and the Mild Behavioral Impairment Checklist (MBI-C). We will explore the possible associations between apathy, blood biomarkers, and the therapeutic potential of NAC in these patients.

White matter lesions is the key neuroimaging finding defining probable mild VCI. We will define those with clinical symptoms indicating vascular disease, and negative neuroimaging findings as possible mild VCI. We hypothesize that patients with probable mild VCI will have higher OS than patients with possible mild VCI. We will explore baseline brain GSH levels in patients with probable mild VCI compared to patients with possible mild VCI. Where possible, we will also test our primary and secondary outcomes in the probable mild VCI subgroup.

Oxylipins are lipid species formed from the oxygenation of polyunsaturated fatty acids; they play a role in inflammation and vascular function. Oxylipins will be explored in association with cognitive and mood symptoms. Mitochondrial dysfunction has been linked to inflammation and several diseases including Alzheimer's disease and cardiovascular disease. Mitochondrial dysfunction will be measured by circulating cell-free mitochondrial DNA (**ccf-mtDNA**). We will explore its relationship with blood biomarkers, cognition, and neuroimaging biomarkers.

Placental growth factor (**PIGF**) is a protein belonging to the vascular endothelial growth factor family and higher levels are associated with CAD. It is proposed to stimulate angiogenesis as a response to pathological events, such as cardiovascular disease and ischemia, and can be enhanced through exercise. We will explore the clinical relevance of PIGF, its relationship with neuroimaging biomarkers, and its relationship with cognition. Astrocyte performs a crucial role in central GSH synthesis and homeostasis. Astrocyte depletion may be a biomarker of OS mediated astrocyte dysfunction that precipitates change in brain GSH. Astrocytic damage and dysfunction will be quantified by measuring the S100 calcium-binding protein B (S100B). S100B is a biomarker secreted by astrocytes that enters the bloodstream^66. Evidence shows that S100B was consistently elevated in the brain, cerebrospinal fluid and serum among mild/moderate AD. We will explore possible associations between S100B and brain GSH levels.

Recent studies suggest a role of innate immune activity, including the effects of neutrophils, in neurodegeneration and cognitive decline. Myeloperoxidase (MPO), an enzyme primarily found in the auzophilic granules of neutrophils, catalyses the formation of reactive oxidant species (ROS). Previous research has reported higher blood concentrations of MPO in CAD patients and serum MPO concentration has been associated with future risk of developing CAD. High concentration of peripheral MPO have also been reported in individuals with vascular dysfunction, such as high WMH burden and AD. We will explore possible associations between MPO and specific cognitive domains. Examining this relationship will enable us to identify upstream contributors of inflammation and OS associated with symptoms of mVCI.

## 4 METHODS

### 4.1 Study Design

This is a 24-week randomized, double-blind, placebo-controlled parallel group design study involving mild VCI patients to evaluate the efficacy and safety of oral NAC supplementation (2,400 mg daily) as an add-on therapy to improve cognitive function in patients undergoing cardiac rehabilitation (**CR**). The CR program consists of a harmonized aerobic and resistance training in a supervised group setting. Eligible patients will be randomized to receive NAC (four 600 mg capsules given as 2 capsules in the morning and 2 capsules in the evening) or matching placebo capsules. The initial NAC dosage will be 600mg/day (one 600mg capsule in the morning) for the first week, followed by 1,200 mg/day (one 600 mg capsule in the morning, one 600mg capsule in the evening) for the second week, followed by 1,800 mg/day (two 600mg capsules in the morning, one 600mg capsule in the evening) for third week, followed by 2,400mg/day (two 600mg capsules in the morning, two 600mg capsules in the evening) for the following 21 weeks.

### 4.2 Subjects

This study will be approved by the Research Ethics Board of Sunnybrook Health Sciences Centre (Sunnybrook) and the University Health Network (UHN). All patients will provide written, informed consent.

**Mild VCI** will be diagnosed by a clinical history of vascular disease, the presence of mild cognitive impairment as defined by modest deficits (1 SD below population norm) in executive function, memory, processing speed or working memory. Subjects will be categorized as “possible mild VCI”, those that meet neuroimaging criteria (below) will be categorized as “probable mild VCI”.

**Probable mild VCI** will be diagnosed using the core diagnostic criteria for Subcortical Ischemic Mild Cognitive Impairment, which include (A) Presence of mild cognitive impairment, as defined by modest deficits (1 SD below population norm) in executive function, memory, processing speed or working memory; (B) Absence of prior symptomatic stroke (silent brain infarcts are allowed); (C) Presence of “diffuse, subcortical cerebrovascular disease”, defined as 1) the presence of two or more silent brain infarcts in supratentorial locations or 2) extensive white matter disease (Age-Related White Matter Change [**ARWMC**] scale score of 2 or higher, indicating “beginning confluence of lesions” or greater) in any brain region.

## 5 PARTICIPANT SELECTION AND WITHDRAWAL

A total of 60 mild VCI patients will be recruited from the CR program at the University Health Network Toronto Rehabilitation Institute.

### 5.1 Inclusion Criteria

Each mild VCI participant must meet all of the following inclusion criteria at baseline:

- Males or females aged 55-85 years.
- MoCA score indicating cognitive impairment (less than 28 out of 30; Telephone MoCA: less than 20 out of 22)
- Modest deficits (1 SD below population norm) in executive function, memory, processing speed or working memory based on the 60-minute battery recommended by the NINDS-CSN.
- Speaks and understands English.
- Enrollment in the Cardiac Rehabilitation program at the University Health Network Toronto Rehabilitation Institute.

In addition, to meet criteria for **probable mild VCI**

- Presence of “diffuse, subcortical cerebrovascular disease”, defined as 1) the presence of two or more silent brain infarcts in supratentorial locations or 2) extensive white matter disease (Age-Related White Matter Change [**ARWMC**] scale score of 2 or higher, indicating “beginning confluence of lesions” or greater) in any brain region.

Participants who exhibit modest deficits (1 SD below population norm) in executive function, memory, processing speed or working memory based on the 60-minute battery recommended by the NINDS-CSN but do not have MRI findings of “diffuse, subcortical cerebrovascular disease” will be categorized as **possible mild VCI**.

### 5.2 Exclusion Criteria

All participants meeting any of the following exclusion criteria at baseline will be excluded from participation in this study:

- A history of stroke
- A history of epilepsy
- Uncontrolled asthma (requiring hospitalization or ER visit in the last 3 months by patient report)
- Uncontrolled diabetes (clinical determination)
- Severe hypo/hypertension (clinical determination)
- Uncontrolled hypercholesterolemia (clinical determination)
- Presence of significant medical illnesses:
  - Severely disturbed liver function
  - Severely disturbed kidney function
  - Severely disturbed lung function
  - HIV, HBV and/or HCV infection
  - Malignant tumors

- A current neurological condition
  - Parkinson's disease
  - Multiple sclerosis
  - Significant traumatic brain injury
- Major psychiatric condition
  - Current major depressive disorder
  - Schizophrenia
  - Bipolar disorder
  - Substance use disorder (alcohol abuse, heavy smoking (20 cigarettes or more/day))
- Contraindication to MRI or MRS (e.g. metal in body, pacemaker).
- Contraindication to NAC (documented allergy) or allergy to lactose.
- Daily nitroglycerin use.
- Bleeding disorders (e.g. hemophilia, thrombotic thrombocytopenic purpura) and/or elective surgery within 30 days.
- Volunteers who currently participate in another pharmacological study.

### **5.3 Participant Recruitment**

Participants will be recruited for the study from the cardiac rehabilitation program at Toronto Rehabilitation Institute. Study personnel will make initial contact with potential subjects and will explain all the details of the study. Participants will be given as much time as they need to review the information sheet and consent form in order to make an informed decision to consent to participate in the study.

### **5.4 Participant Withdrawal and Discontinuation of IP**

#### **5.4.1 Reasons for Withdrawal/Discontinuation of IP**

At their own discretion, participants may withdraw from the study at any time and for any reason. Study participants will be withdrawn from the study if consent is withdrawn, and will be considered for study withdrawal for non-compliance, significant protocol violation, NAC intolerance and/or severe adverse events, the development of new medical conditions which prevent the continuation of participation, being uncooperative during the study, or if continuing in the study is in conflict with the best interest of the patient. Any patients with emergent AEs will be followed until the AEs are resolved.

#### **5.4.2 Data Collection and Follow-up for Withdrawn Participants**

Participants who withdraw from the study will be contacted by the study research team to request a final visit and to follow up any unresolved adverse events. After the early termination visit, no further study procedures or evaluations will be performed, or additional study data collected. Any data collected prior to the withdrawal of consent may be retained and used by the sponsor.

## 6 INTERVENTIONS

### 6.1 Investigational Product

N-acetylcysteine (NAC), Natural Health Products Directorate (NPN #: 80004844), supplementation will be used as an add-on therapy to improve cognitive function in patients undergoing cardiac rehabilitation.

#### 6.1.1 *Intervention*

Patients will be randomized to receive NAC (four 600 mg capsules given as 2 capsules in the morning and 2 capsules in the evening) or matching placebo capsules. The initial NAC dosage will be 600mg/day (one 600mg capsule in the morning) for the first week, followed by 1,200 mg/day (one 600 mg capsule in the morning, one 600mg capsule in the evening) for the second week, followed by 1,800 mg/day (two 600mg capsules in the morning, one 600mg capsule in the evening) for third week, followed by 2,400mg/day (two 600mg capsules in the morning, two 600mg capsules in the evening) for the following 21 weeks. The dose will be escalated (to 2,400mg), unless there are tolerability issues (assessed by QI), in which case the QI will decide which dose is appropriate for the patient.

The Pharmacy Department at Sunnybrook Health Sciences Centre will prepare, label and dispense the experimental and placebo (lactose-filled) capsules. The Pharmacy Department at Sunnybrook Health Sciences Centre will prepare the placebo capsules by using empty capsule shells supplied by SISU, a Canadian manufacturer, and filling them with a lactose-based filler. To make experimental and placebo capsules indistinguishable with regard to taste and appearance, a process will be implemented to mimic the smell of NAC, as done previously. The investigational product and placebo capsules will be stored in a secure location at Sunnybrook in a temperature monitored area. Placebo and intervention capsules will be provided by SISU, and licensed in accordance with Natural Health Products Regulations. Details regarding this preparation will be filed in the Natural Health Products Directorate (NPN #: 80004844). The Pharmacy Department at Sunnybrook Health Sciences Centre will destroy the experimental and placebo capsules.

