
## 7.4 Statistical Analyses

All analyses will be performed using current versions of SPSS and SAS (SAS Institute, Cary, NC, USA). The intention-to-treat analyses will be based on data from all patients who undergo randomization, meet the inclusion criteria for the study, receive the trial medication at least once, and undergo at least baseline observation. Descriptive statistics will be calculated for composite z-scores for executive function, memory, and speed of processing. Categorical variables will be summarized using counts and percentages. Continuous variables will be compared between groups using two sample two sided t-tests (or Wilcoxon rank sum tests for non-normal data), whereas categorical variables will be compared between groups using chi-square analyses or Fisher's exact tests.

Primary Hypothesis: Differences in executive function composite z scores between the groups at 24 weeks will be compared between treatment groups using a two sample two sided t-test. A linear mixed model will be run to compare the rate of change in the executive function measure over time (baseline, 12- and 24-weeks). The linear mixed model is selected as it can accommodate missing data in subjects. The effects of age, sex, BMI, total years of education, VO2 peak, physical activity levels, serum homocysteine, will be included as possible covariates. The same analyses will be repeated with the composite z-scores of the other cognitive domains as repeated variables to test for the effect of NAC treatment on the secondary outcome measures.

Secondary Hypotheses: A linear mixed model will also be used to test the hypothesis that patients with mild VCI treated with NAC will show a greater reduction in 8-ISO/LPH ratio over 24 weeks of treatment. The early to late stage lipid peroxidation marker ratio will be inputted as the repeated variable, and treatment group will be added as a fixed factor. The effects of group by time interaction will be evaluated to indicate significant effects of NAC in reducing oxidative stress markers as compared to placebo. APOE4 genotype status, BMI, VO2 peak, and sex will be added as covariates. Similar analyses will be conducted separately with GPx, GR and GST inputted as the repeated variable. Logistic regression analyses will be performed to examine whether baseline severity of WMH is a significant predictor of cognitive response to NAC treatment at 24 weeks, adjusting for the same covariates.

Exploratory Hypothesis:

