
A linear mixed model will be used to assess baseline brain GSH as a predictor of change in executive function, processing speed, memory and working memory composite z scores over 24 weeks in patients with mild VCI. A GSH x time interaction will indicate a significant relationship between brain GSH and change in executive function, processing speed, memory and working memory performance over time.

Post-hoc analyses will be used to assess change in 8-ISO/LPH ratio over 24 weeks of treatment between possible and probable mild VCI subgroups using linear mixed models. Between group differences in baseline brain GSH levels will also be assessed using analyses of covariance. Where possible, the primary and secondary hypotheses will also be tested in the probable and possible mild VCI subgroups and compared.

Linear regression will be used to investigate baseline serum S100B as a predictor of baseline brain GSH levels, and if serum S100B at baseline will predict change in brain GSH over a 6-month period. Body fat percentage will be included as a potential confounder in this analysis.

Linear regression will be used to assess association between mitochondrial dysfunction as measured by ccf-mtDNA and oxidative stress markers at baseline and over time. A linear regression model will be used to investigate the association between PIGF, oxidative stress markers at baseline and termination. A linear regression model will be used to investigate peripheral MPO as a predictor of executive function or verbal memory at baseline. Age, use of anti-inflammatory medications and inflammatory and vascular comorbidities will be included as covariates. Measures of mood, cognitive function, and metabolic markers (oxylipins) will be compared between the baseline and follow-up visits, and changes in these measures will be compared between individuals relative to each other in a repeated measures linear regression analyses.

**Safety Outcomes:** Frequency of adverse events between treatment and placebo groups will be compared using chi-square/ Fisher exact tests. In addition, exploratory analyses using logistic regression will be performed to determine predictors of cognitive response to NAC, including demographics and compliance.

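### A patient who cannot tolerate the capsules may be put on a lower dose or withdrawn from the study; no rule says which, and withdrawal loses the 24-week outcome

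*Combined protocol and SAP*

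**What the plan says.** Three sections of the protocol deal with a patient who does not tolerate the capsules.

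- **6.1.1 Intervention.** The dose rises over three weeks to 2,400 mg/day, "unless there are tolerability issues (assessed by QI), in which case the QI will decide which dose is appropriate for the patient". The patient stays in the study. No minimum dose or stopping criterion is given.
- **5.4.1 Reasons for Withdrawal/Discontinuation of IP.** Participants "will be considered for study withdrawal for non-compliance, significant protocol violation, NAC intolerance and/or severe adverse events". The heading names discontinuation of the product, but the text deals only with leaving the study.
- **5.4.2 Data Collection and Follow-up for Withdrawn Participants.** A final visit is requested and unresolved adverse events are followed. Then: "After the early termination visit, no further study procedures or evaluations will be performed, or additional study data collected". The content of that visit is not stated, and neither Appendix A nor Appendix B has a column for it.

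Section 6.1.4 is the nearest thing to a retention rule. It keeps non-compliant patients (under 80% of capsules) in the study unless the investigators have safety concerns.

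The analyses that depend on this are in 7.4 and 3.2. Executive function "composite z scores between the groups at 24 weeks will be compared between treatment groups using a two sample two sided t-test", and a linear mixed model compares "the rate of change in the executive function measure over time (baseline, 12- and 24-weeks". The intention-to-treat set is all randomised, eligible patients with at least one dose and a baseline observation. For tolerability, 3.2 expects that "measures of safety (including incidences of adverse events and drop-outs) will be comparable between treatment with NAC and placebo", and 7.4 says "Frequency of adverse events between treatment and placebo groups will be compared using chi-square/ Fisher exact tests".

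**The concern.** The same clinical event can be handled in two ways that leave different data behind. On the lower-dose route the patient reaches Week 24 and counts in every analysis. On the withdrawal route the patient has no 24-week score.

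The loss is unlikely to be random, because the reason for it is a reaction to the capsules. If NAC causes more intolerance than placebo, the 24-week comparison sets NAC patients who tolerated the drug against a nearly complete placebo arm, under an intention-to-treat label. Recruiting 60 patients replaces lost numbers; it does not correct losses that differ by arm.

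The route also decides a named safety result. An intolerant patient counts as a drop-out only if withdrawn, so similar drop-out rates could reflect good tolerability or simply reduced doses. No planned table shows which.

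**Working it through.** **Step 1. Follow an intolerant patient down each route.**

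| | Kept on a lower dose (6.1.1) | Withdrawn from the study (5.4) |
|---|---|---|
| 24-week t-test | score available | no score |
| Mixed model (baseline, 12, 24 weeks) | all scores | scores up to withdrawal; only baseline if gone before Week 12, unless the final visit happens to include the battery |
| Drop-out count (3.2) | not counted | counted |
| Adverse events (7.4, 8.3) | recorded | recorded |

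The dose is raised during Weeks 1 to 4 and the first post-baseline battery named in 7.4 is at 12 weeks. A patient who leaves during titration therefore has no scheduled post-baseline score.

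**Step 2. Inputs.** From 7.5: SD 0.55, a medium effect (no number given) and 60 patients. The plan's 60 reproduces as 42 × 1.42 = 59.64. Whether that is the right inflation is a separate question; this point does not rest on it. The plan gives no intolerance rate, so the following are assumptions:

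- 30 patients per arm and no other losses;
- p = share intolerant on NAC: 3, 6 or 9 of 30 (0.1, 0.2, 0.3);
- D = full-dose effect: 0.5 SD, or 0;
- f = share of the effect kept at a reduced dose: 0 to 0.5;
- δ = how much lower such patients score at 24 weeks on either arm: 0 to 0.5 SD;
- the placebo arm holds the same share of these patients, and they stay.

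**Step 3. Expected 24-week difference.** The placebo mean is −pδ.

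- All kept: [(1 − p)D + p(fD − δ)] − (−pδ) = D(1 − p + pf).
- All withdrawn on NAC: D − (−pδ) = D + pδ.

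With D = 0.5:

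| Intolerant on NAC | All kept (f = 0 to 0.5) | All withdrawn (δ = 0 to 0.5) |
|---|---|---|
| 3 of 30 | 0.45 to 0.48 SD | 0.50 to 0.55 SD |
| 6 of 30 | 0.40 to 0.45 SD | 0.50 to 0.60 SD |
| 9 of 30 | 0.35 to 0.43 SD | 0.50 to 0.65 SD |

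In z units at 6 of 30 (× 0.55), that is 0.22 to 0.25 against 0.28 to 0.33. Only pδ is bias. The rest of the gap is a change of target: the effect of being assigned NAC, low doses included, against the full-dose effect in those who tolerate it.

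**Step 4. With no true effect (D = 0).** The kept route has no bias. The withdrawal route has pδ, which at δ = 0.5 is 0.05, 0.10 and 0.15 SD for 3, 6 and 9 of 30. At 6 of 30, simulating the t-test with 24 against 30 patients gives about 6.3% false positives, against 4.5% when all are kept. The standard error of the difference is √(1/24 + 1/30) = 0.27 SD, so a bias of 0.10 SD is well under half a standard error.

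**Step 5. The drop-out measure.** Assume also 1 of 30 intolerant on placebo. All withdrawn: 6/30 against 1/30, a difference of 17 percentage points (Newcombe 95% interval −0.3 to 34; Fisher p = 0.10). All kept: 0 against 0. The underlying intolerance is the same.

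**The case against.** The strongest reply is that the sections can be read in sequence: 6.1.1 gives the response to intolerance, and 5.4.1 only allows withdrawal to be considered if that fails. Blinded clinical judgement at one centre is ordinary practice. This is a fair reading, and the fix adopts its first step. But the text does not state it, and even then the second step is leaving the study rather than stopping capsules. Blinding prevents knowing, arm-specific decisions; it does not make intolerance equally common in both arms.

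Other text narrows the point:

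- Section 6.1.4 keeps non-compliant patients absent safety concerns, and 8.6 mentions stopping the drug as an act of its own after overdose. Both lean towards retention, but neither covers intolerance.
- The mixed model keeps scores obtained before withdrawal. If the intolerant patients' deficit is already there at baseline, a change analysis would largely remove it for those with a later score. It cannot do so for patients who leave before Week 12, and it does not repair the t-test.
- The intolerance rate may be low. The protocol says "Previous trials have shown that NAC at these doses is well-tolerated in the elderly". At 3 of 30 the two routes differ by only 0.025 to 0.10 SD.
- All kept against all withdrawn is the extreme contrast; case-by-case decisions would fall between.

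These replies limit the size of the problem. They do not remove the gap.

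**Conclusion.** The point holds as a gap worth closing, not as a flaw that invalidates the trial. Intolerance has two routes with no rule between them, and one of them loses the primary outcome for a reason that may differ by arm. The bias with no true effect is at most 0.10 SD at 6 of 30, with about 6% false positives. That rests on assumed rates, all intolerant NAC patients being withdrawn, and a deficit of no more than 0.5 SD. It scales with the rate, from 0.05 SD at 3 of 30 to 0.15 SD at 9 of 30.

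A reader might infer more than the documents support:

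- *That withdrawal yields no further data.* A final visit is requested and adverse events are followed. What is missing is a stated content for that visit and a 24-week score.
- *That intolerance would be hidden if doses were lowered.* It is recorded as an adverse event on either route, from a symptom checklist. Only the drop-out measure depends on the route.
- *That 3.2 sets a full-dose tolerability objective.* The reference to dose is in the background sentence on previous trials; the hypothesis compares NAC with placebo.
- *That reduced-dose patients fall outside the primary analysis.* The intention-to-treat definition does not exclude them.

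**What to change.** In 6.1.1 and 5.4, state one pathway. For intolerance, the qualified investigator lowers the dose first. If the lower dose is still not tolerated, capsules are stopped but the patient stays in follow-up, with the cognitive battery at Weeks 12 and 24. Reserve study withdrawal for withdrawn consent, or for when further assessment is unsafe or impossible. Specify that the early termination visit includes the battery, and show that visit in both schedules.

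In 3.2 and 7.4, report by arm the numbers with dose reduced or not escalated for tolerability, with capsules stopped, and who left the study.

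The cost is protocol wording, one schedule column, one table, and Week 12 and 24 visits for those who stop capsules (at most about 6 NAC patients at the 6 of 30 assumed above). Some of them may decline to attend off treatment. The estimated effect may also be smaller, because it will include patients on a low dose or none.
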